1.1 Primary Feasibility Objective

To determine feasibility for a larger clinical trial in women at moderately increased risk we will:

1.1.1 Determine if accrual is brisk as demonstrated by accrual of at least 20 moderate risk women in the initial 6 months (3.5 entrants per month) in a single institution;

1.1.2 Determine if there is a 15% or lower dropout rate over the 6 month intervention; and

1.1.3 Determine if 20% or fewer women with paired RPFNA specimens exhibit a meaningful increase in benign breast cell proliferation (Ki-67) where meaningful increase is defined as an increase in Ki-67 to 2% or higher in individuals with initial Ki-67 < 1% or a doubling of Ki-67 in individuals with initial Ki-67 of 1% or higher.

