1.2 Secondary Exploratory Objectives

A number of analyses will be conducted in an effort to document and describe the effects of Duavee® on a variety of variables that are actual or potential risk biomarkers for development of breast cancer.

- Assess benign breast tissue for decrease in Ki-67 in women with Ki-67 of 1% or higher
- Assess changes in benign breast tissue estrogen responsive genes by RTqPCR
- Assess changes in benign breast tissue peptides and phosphopeptides.
- Assess changes in serum bioavailable hormones and cytokines
- Assess change in bazedoxifene serum levels as a function of BMI, percent body fat, and compliance (by tablet count)
- Document change if any in body composition (DEXA), and waist circumference
- Document change if any in volumetric breast density (Volpara) and compare to % dense area (Cumulus)

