8. CRITERIA FOR EVALUATION AND ENDPOINT DEFINITION

8.1 Primary Endpoint

Prior to formal analysis, there are two aspects of a feasibility trial that are based on simple numbers. If we cannot accrue 40 eligible women within a reasonable time (no more than 12 months) and/or if more than 15% of enrolled participants do not complete the study, then it would not be practical to propose future studies.

For the Specific Aim of documenting that Duavee® does not cause a meaningful increase in proliferation, only participants for whom paired specimens evaluable for Ki-67 will be included. An increase in Ki-67 will be defined by one of two scenarios: a) from a baseline Ki-67 <1% to a Ki-67 >2%; or b) for a baseline Ki-67 >1%, at least a doubling of the baseline value.

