8.2 Secondary Endpoints

For the second Specific Aim (Does Duavee® cause a reduction in Ki-67?), we will consider only participants having baseline Ki-67 >1%; and thus the potential to experience a decrease.

Any remaining assessments of modulation due to Duavee® would be considered exploratory for purposes of informing future applications and trial designs. This would include change in breast cytomorphology index score; changes in gene expression (specifically, pS2, PGR, ER alpha, GREB-1, Amphiregulin, SDF-1, cyclin D1) by RTqPCR; changes in levels of ER alpha and cyclin D1 and possibly other proteins and phosphoproteins by proteomics; change in serum bioavailable hormones, adipocytokines, and change in menopause specific quality of life. For these analyses, all participants with paired pre-study and post-study data will be included.

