13.2 Primary Feasibility Endpoints

The primary endpoint overall is an assessment of feasibility that will inform the decision about and the design of subsequent trials. This will be based on considerations of 1) ease of accrual of the target population; 2) acceptance and tolerability of the intervention. Basically, if either fail, then it would indicate that future trials with this approach are not feasible to consider

For the first aspect of accrual, a criterion has been set at 20 participants accrued in 6 months (starting from when the trial is actually open to enrollment). If the accrual rate is slower than this, it would be impractical to conduct a similar trial at a single institution. While total accrual will be used for this initial criterion, the relative ease of accrual into the two cohorts (Cohort A, Ki-67<1%; Cohort B, 1% ≤ Ki-67 < 4%) will be taken into consideration. Certainly it is anticipated that accrual to Cohort A will be easier and faster, but if accrual to Cohort B is not at least half the overall rate (i.e., 20 participants per 12 months) then it would indicate that a trial requiring measurable Ki-67 >1% would not be a feasible option. For this assessment, accrual is considered as meeting all eligibility criteria, signing an informed consent, and receiving the first dose of study agent. This number will then be used for consideration of the second feasibility aspect.

The second aspect of feasibility is retention of participants on trial, completion of the planned 6 months of intervention, and acquisition of repeat RPFNA specimen (plus blood, mammogram, etc.) for assessment of modulation in quantitative biomarkers. A criterion has been set at 85% completion overall. While the ultimate goal is paired samples for comparison of biomarkers (for sample size and power calculation purposes), a high incidence of early problems with participant compliance in general (adverse events, complaints about the study agent or the schedule, etc.) would serve as an indication that the intervention would not be suitable for future trials.

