13.3 Primary Quantitative Endpoint

The primary quantitative (but secondary overall) endpoint addresses the specific question that Duavee® might produce the deleterious effect of increasing breast cell proliferation. While there is no evidence for this (and the FDA does not consider this a risk to be included in labelling) it is still a perceptual concern by women and providers. Thus, an assessment will be made of the frequency of participants that exhibit a likely clinically meaningful increase in Ki-67. This will be defined differently for the two cohorts, but both will contribute to the analysis of potential increase. For Cohort A (initial Ki-67 < 1%), a meaningful increase is defined as any value of 2% or greater on the off-study aspiration. For Cohort B (initial Ki-67 \geq 1% but <4%), a meaningful increase is defined as a doubling or greater of the initial rate (i.e., a repeat aspiration value of at least 2%). Historically, for women in our High Risk Breast Clinic similar to those being enrolled in this study, approximately an 11% incidence of Ki-67 increasing is observed in the absence of any intervention. Therefore, with a minimum (per feasibility endpoint #2) of 34 paired specimens in which to assess change, an observed frequency of 10% or less would provide assurance that the true rate does not exceed 20% (95% confidence interval). Conversely, an observed frequency as high as 20% could still accommodate a true rate of 10%. Thus, as long as the observed frequency is \leq 20%, subsequent trials could be designed with a placebo-control arm. Only for an observed frequency >20% would it be impractical to design future biomarker trials.

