13.4 Secondary Exploratory Endpoints

This study is not specifically powered to address the objectives of estimating favorable change in quantitative biomarker endpoints that may be related to risk for development of breast cancer.

The most critical biomarker from a breast cancer prevention standpoint is that of cell proliferation, specifically a reduction in value for participants whose baseline specimen exhibited sufficient Ki-67 staining (1% that there is the potential for a decrease). Thus, this analysis will be limited to those participants in Cohort B. Also this parameter will be analyzed first and separately from all other biomarkers. Descriptive statistics will be used to summarize the values of Ki-67 (percent of cells staining positive) in the baseline specimen, the 6-month (off-study) specimen, and the change (both absolute and relative) from baseline to off-study. For statistical analysis, the Wilcoxon signed-rank test will be used to accommodate the expected small sample size and to avoid any assumptions regarding normal distributions. Only participants who provide paired specimens evaluable for Ki-67 will be included in this analysis. However, for off-study specimens where the cell yield is so low (<100 cells per slide) that assessment of Ki-67 is not even possible, an anti-proliferative effect can be inferred. Thus, a value of 0.5% will be imputed as a reasonable compromise between imputing a value of 0% (no evidence of any proliferation) and a value of 1% (e.g., only 1 positive cell out of 100 counted). Since a non-parametric approach is used, the exact imputed value has minimal impact given that the criterion for inclusion is a baseline value of 1%. For this primary evaluation of modulation of a quantitative measure, $p < 0.05$ will be considered the criterion for statistical significance.

Should there be adequate, paired specimens, further exploration of this primary endpoint variable, relative change in Ki-67, will be accomplished by developing an appropriate model and testing covariates. If necessary, an appropriate transformation will be used in this regression.

For these possible analyses, as for the exploratory analyses below, no adjustment will be made for multiple comparisons, but the results will be interpreted with caution.

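### Section 8.1 sets the Ki-67 increase limits at >2% and >1%, while 1.1.3 and 13.3 include 2% and 1%; under 8.1 a woman with baseline exactly 1.0% can never be an event

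*Combined protocol and SAP*

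**What the plan says.** The event is defined in three places.

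- **1.1.3 (objective):** "an increase in Ki-67 to 2% or higher in individuals with initial Ki-67 < 1% or a doubling of Ki-67" in women starting at 1% or higher. The success criterion is that at most 20% of women with paired specimens are events.
- **13.3 (statistical section):** for Cohort A, any follow-up of 2% or more. For Cohort B, which here includes 1%, "a meaningful increase is defined as a doubling or greater of the initial rate (i.e., a repeat aspiration value of at least 2"%).
- **8.1 (endpoint definition):** "a) from a baseline Ki-67 <1% to a Ki-67 >2%; or b) for a baseline Ki-67 >1%, at least a doubling" of the baseline value. All women with paired evaluable specimens enter this analysis.

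Section 13.2 sets the cohorts as "Cohort A, Ki-67<1%; Cohort B, 1% ≤ Ki-67 < 4"%, with no gap at 1%. Later in the same paragraph it describes Cohort B loosely: "a trial requiring measurable Ki-67 >1% would not be a feasible option".

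The secondary question, whether Ki-67 falls, has the same split. Section 1.2 reads "Assess benign breast tissue for decrease in Ki-67 in women with Ki-67 of 1% or higher", and 13.4 says "this analysis will be limited to those participants in Cohort B". In 8.2, however, "we will consider only participants having baseline Ki-67 >1"%.

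Section 9.1.1 has 500 ductal cells scored per specimen.

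**The concern.** Under 8.1 as written, a baseline of exactly 1.0% is neither below nor above 1%. The woman is in the denominator, but no follow-up value can make her an event: 1.0% to 10% does not count, while 1.2% to 2.4% does. Section 13.2 places her in Cohort B, where 13.3 would count any doubling. A rise from below 1% to exactly 2.0% is an event under 1.1.3 and 13.3 but not under 8.1.

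Both differences reduce the number of increases, and the trial is meant to show that increases are uncommon. Section 13.3 says that a frequency above 20% would make future biomarker trials impractical. An analyst who codes the endpoint from the section that defines endpoints could therefore report a pass where the 1.1.3 rule gives a fail.

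In the secondary analysis the same woman is in the Wilcoxon test by 1.2 and 13.4 and out of it by 8.2.

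**Working it through.** **1. The plan's own figures.** 40 enrolled (13.2) × 85% completion (13.2) = 34 pairs, as 13.3 states. The 13.3 statement that an observed 10% excludes a true rate above 20% is reproduced to rounding by the normal approximation: 0.10 + 1.96 × √(0.10 × 0.90 / 34) = 0.10 + 0.101 = 20.1%.

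**2. The decision limit in whole women.** 0.20 × 34 = 6.8, so at most 6 events pass: 6/34 = 17.6% and 7/34 = 20.6%. If 36 complete, as section 3 expects, 7/36 = 19.4% passes and 8/36 = 22.2% fails. In either case one reclassified woman can change the result.

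**3. The measurement grid.** One cell in 500 is 0.2%. So 5/500 = 1.0% and 10/500 = 2.0% exactly. A baseline below 4% (4.3.1) means 0 to 19 positive cells.

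**4. The two rules side by side.** Let b and f be the positive cells out of 500 at baseline and follow-up.

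| Baseline | Event under 1.1.3 and 13.3 | Event under 8.1 |
|---|---|---|
| b = 0 to 4 (below 1%) | f ≥ 10 | f ≥ 11 |
| b = 5 (exactly 1.0%) | f ≥ 10 | never |
| b = 6 to 19 (1.2% to 3.8%) | f ≥ 2b | f ≥ 2b |

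Over all b from 0 to 19 and f from 0 to 500, the rules disagree in 5 × 1 + (500 − 10 + 1) = 496 combinations, 491 of them at b = 5. In every one the pair is an event under 1.1.3 and not under 8.1; the reverse never occurs.

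**5. How often the boundary is hit.** If cell counts are binomial, P(5 of 500 | true 1%) = 0.176 and P(10 of 500 | true 2%) = 0.126. For true values of 0.5% and 2.0%, P(5 of 500) is 0.067 and 0.037.

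**6. Effect on the verdict.** The documents give no joint distribution of baseline and follow-up Ki-67, so this step rests on assumptions: 500 cells; true Ki-67 gamma-distributed with mean 1.0-1.4% and between-woman CV 0.7-0.8; within-woman CV 0.3-1.2; true change 1- to 3-fold; baseline below 4%. In all, 168 settings were simulated, with 300,000-400,000 pairs each. Because every 8.1 event is also a 1.1.3 event,

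P(verdict changes) = P(X > 6 | n = 34, 1.1.3 rate) − P(X > 6 | n = 34, 8.1 rate).

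Baseline was exactly 1.0% in 5.5-8.9% of women (about 2-3 of 34), or 15-21% of Cohort B.

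| 1.1.3 event rate | Trials in which the verdict changes | Chance of observing more than 20% is multiplied by |
|---|---|---|
| 10-12% | 3-7% | not tabulated |
| 18-22% | 18-31% | 0.46-0.66 |
| 22-26% | 19-29% | 0.57-0.76 |
| 30-36% | 5-18% | 0.80-0.95 |
| above 40% | at most 2.5% | at least 0.97 |

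Worked example (mean 1.0%, CVs 0.7 and 0.3, 1.75-fold change): the event rate is 21.0% under 1.1.3 and 15.6% under 8.1. Then P(X > 6) is about 0.59 and 0.27, a difference of about 0.32. Simulating 40,635 whole trials of 34 women in this setting gave 58.8% and 26.9%, with the verdict changed in 31.8% and never in the reverse direction.

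**7. Sensitivity to the assumed mean.** With mean Ki-67 of 0.3-0.7%, the share at exactly 1.0% falls to about 2.6-7.4%. The figures by event rate stay roughly as tabulated. At means of 0.3-0.5% with 1- to 2-fold change, the verdict changes in 0-8% of trials.

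**The case against.** - **A sign may have been lost when the PDF was read.** An underlined > would explain 8.1 and 8.2 together. The text of 13.4 is visibly damaged at this same cut-off, and the Schema writes >500 cells where it elsewhere means 500 or more. This cannot be excluded. Against it, a ≤ sign survives in 13.2 and a code for ≥ in 13.3, so the finding concerns the text as it reads.
- **The intended rule is clear.** Sections 1.1.3, 13.2 and 13.3 agree with each other, and 13.3 is the section that specifies the analysis. This stands. It makes the repair easy, but it does not remove a conflicting rule from the endpoint-definition section.
- **Two of the edits correct no endpoint rule.** The >1% in 13.2 describes a possible future trial. The bracket in 13.3 is true of any doubling from 1% or more, although it equals a doubling only at baseline 1.0%. This also stands: they are loose wording that could be miscoded, not further rules.
- **The size is assumption-driven.** The only event rate in the documents is about 11% without intervention (13.3), where the verdict changes in 3-7% of trials. A mean of 1.0-1.4% is high against the 0-1% that section 2.3 cites for normal postmenopausal epithelium. The exact grid is also uncertain: 4.3.1 allows more than 500 cells, 13.4 treats Ki-67 as unassessable only below 100 cells, ducts are chosen for high staining, and the derivation of the consensus score is not described. All of this is fair, but the direction of the error and the contrast of 6/34 with 7/34 need no model.
- **The stakes are modest.** Section 13.3 calls this endpoint secondary overall, and 13.2 disclaims conclusive proof. However, 1.1.3 lists it under the primary feasibility objective and 8.1 is headed as the primary endpoint.

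**Conclusion.** The concern holds, with high confidence, for the text as written, and it should be fixed. Section 8.1 contradicts 1.1.3, 13.2 and 13.3 at both boundaries, and 8.2 contradicts 1.2 and 13.4 at 1%. Without any distributional assumption, the 8.1 rule can only reduce the event count, and a single boundary case among 7 events in 34 turns a fail into a pass.

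How often that would happen depends on the assumed Ki-67 distribution and on the 500-cell grid. It is material when the true event rate is near 20%, small near the 11% background rate, and negligible if the drug produces a large increase.

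**What to change.** Use the 1.1.3 rule throughout: baseline <1% and follow-up ≥2%, or baseline ≥1% and follow-up at least twice baseline.

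1. In 8.1, change >2% to ≥2%.
2. In 8.1, change >1% to ≥1%.
3. In 8.2, replace >1% with the Cohort B definition (≥1% and <4%).
4. In 13.2, make the same replacement in the sentence about a future trial requiring measurable Ki-67.
5. In 13.3, replace the bracketed explanation for Cohort B with: at least twice the baseline value.

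Check the signs in the source document first; any that already read ≥ there need no edit. The cost is wording only: the 40 participants, the 34-pair minimum, the data collected and the burden on participants do not change.

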8.2 Secondary Endpoints

For the second Specific Aim (Does Duavee® cause a reduction in Ki-67?), we will consider only participants having baseline Ki-67 >1%; and thus the potential to experience a decrease.

Any remaining assessments of modulation due to Duavee® would be considered exploratory for purposes of informing future applications and trial designs. This would include change in breast cytomorphology index score; changes in gene expression (specifically, pS2, PGR, ER alpha, GREB-1, Amphiregulin, SDF-1, cyclin D1) by RTqPCR; changes in levels of ER alpha and cyclin D1 and possibly other proteins and phosphoproteins by proteomics; change in serum bioavailable hormones, adipocytokines, and change in menopause specific quality of life. For these analyses, all participants with paired pre-study and post-study data will be included.

8.3 Off Agent Criteria

Participants may stop taking study agent for the following reasons: completed the protocol-prescribed intervention, adverse event or serious adverse event, inadequate agent supply, noncompliance, concomitant medications, medical contraindication, or physician determination. Participants will continue to be followed, if possible, for safety reasons and in order to collect endpoint data according to the schedule of events.

8.4 Off Study Criteria

Participants may go 'off-study' for the following reasons: the protocol intervention and any protocol-required follow-up period is completed, adverse event/serious adverse event, lost to follow-up, non-compliance, concomitant medication, medical contraindication, withdraw consent, death, or participant wishes. If a participant goes off-study for any other reason, details will be recorded.

8.5 Study Termination

A frequency of greater than grade 2 adverse events (exclusive of hot flashes and menstrual irregularities) that exceeds 20% will be cause for consideration of stopping the trial; unless there is adequate information to suggest that the adverse events are not related to the study agent.

9. CORRELATIVE/SPECIAL STUDIES

9.1 Ki-67 and Cytomorphology

Tissue for Ki-67, cytomorphology (4/5 of aspirate), are placed in a modified Cytolyt solution as indicated below and from ~ 1/5th of the aspiration placed immediately in PBS and is immediately frozen in liquid nitrogen for gene and protein expression studies.

9.1.1 Ki-67 Primary Endpoint

Cells are acquired by RPFNA following informed consent. Cells are pooled in a 15 cc conical tube containing 10 cc of formalin modified Cytolyt™ and processed via a liquid based thin layer cell preparation system (ThinPrep™ 2000, Cytoc Corporation). A minimum of two slides will be made: at least one each for cytology and one for Ki-67. Total epithelial cells will be delineated with Mayer's hematoxylin counterstain and proliferating cells with a MIB-1 (DAKO M7240) antibody for Ki-67. We have adapted a staining technique using high temperature antigen retrieval [Khan 2005].

A DAKO automatic stainer will be used for all stains except hematoxylin to insure staining consistency. Ki-67 is visualized as punctate brown dots in the nucleus. Manual counting will be performed by two laboratory technicians employed and scoring assessed by two laboratory technicians. The scores will consist of number of cells assessed, and number of positive cells for Ki-67. Hyperplastic ducts with the highest concentration of MIB-1 positively staining cells will be selected for analysis and 500 total ductal cells will be scored. Numbers of nuclei expressing Ki-67 will be expressed as a percentage of total numbers of cells counted. If hyperplasia is not present in the follow-up specimen at 6 months, non-proliferative areas will be assessed. Cell clusters assessed are viewed with a digital imaging system and representative images archived. A separate score for each technician and a consensus score will be recorded. The consensus score will be utilized for analysis of the primary endpoint.

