trials for over 2 decades [[name] 2000, 2002, 2005, 2007, 2010, 2013]. Similar to diagnostic biopsy series, [Dupont 1985; Hartmann 2014] women with cytologic evidence of hyperplasia with atypia have an increased risk of DCIS and invasive cancer as well as a higher proliferative rate [[name] 2000; Khan 2005]. We observed a median Ki-67 labeling index of 1.4% in RPFNA samples exhibiting hyperplasia with or without atypia from high-risk post-menopausal women in whom there were sufficient cells for Ki-67 to be attempted [Khan 2005]. Inter- and intra-observer variation in interpretation of staining results was low with a Cronbach's alpha of 0.99 [Khan 2005].

A number of antihormonal treatments effective in breast cancer treatment and prevention have been shown to reduce proliferation indices in benign and cancerous breast epithelial cells by 17-50% relative to baseline. [Clarke 1993; Chang 2000; Dowsett 2001; Dowsett 2005; Decensi 2003]. Reduction in proliferation (Ki-67) at two weeks and 12 weeks in the neoadjuvant IMPACT Trial (tamoxifen, anastrozole, combination) was positively associated with disease free survival [Dowsett 2005]. Tamoxifen has been shown to reduce proliferation (Ki-67) in benign breast tissue of postmenopausal women [de Lima 2003]. In a single arm pilot trial six months of the aromatase inhibitor letrozole reduced proliferation by 66% in benign tissue from high-risk women despite continuing hormone replacement [[name] 2007].

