2.5 Mammographic Breast Density as Risk and Response Biomarker

Mammographic density which is composed histologically of ductal and stromal tissue, and fluid is recognized as a risk factor for breast cancer particularly when corrected for age and Body Mass Index (BMI) [Boyd 1993; Boyd 1995; Boyd 1998; Byrne 1995; Warwick 2014]. Although absolute dense area along with % dense area are both risk biomarkers, % density appears to be the stronger risk biomarker [Pettersson 2014]. In a recent analysis, Boyd et al. suggest that women with a high density in the highest tertile of mammographic density corrected for BMI have a risk of 2.63x that of women in the lowest tertile (0-20% density), and women in the mid tertile (20-41%) a risk of 2.15X that of women in the lowest tertile [Boyd 2014]. Given these updated results it is reasonable to include women with an estimated breast density of 25% or higher in the risk criteria for consideration of participation in this study.

Change in mammographic density is validated as a surrogate response biomarkers for trials involving the selective estrogen receptor tamoxifen which is known to reduce risk for breast cancer by 40% or more [Cuzick 2011; Cuzick 2013]. However, change in breast density is not modulated by raloxifene, a selective estrogen receptor modulator known to reduce risk for breast cancer in postmenopausal women almost to the same extent as tamoxifen [Martino 2004; Freedman 2001; Pearman 2010]. Nor is density modulated with exemestane, an aromatase inhibitor that is shown to reduce breast cancer risk by 65%. [Cigler 2011; Goss 2011]. Weight reduction may actually increase percent dense area [[name] 2013; Boyd 1997]. Breast density, even with computer assisted calculations, is subjective and pre and post intervention assessments should be performed by the same individual at the same setting with the rater blinded as to which image was baseline [Stone 2003]. In addition there are a number of technical factors that can introduce error when change is being evaluated including variation in type of imaging, positioning and degree of compression.

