3. SUMMARY OF STUDY PLAN

Peri- or post-menopausal women meeting the risk and medical eligibility criteria (see below) will undergo random periareolar fine needle aspiration (RPFNA) under the umbrella screening protocol HSC 4601. Women with at least 500 cells on their cytomorphology and/or Ki-67 slide, but with Ki-67 expression less than 4% will be eligible to proceed to the intervention phase of this study. At a baseline on-study visit, women will have a physical exam, DEXA for body composition, complete a 29 item Menopause Quality of Life Intervention Questionnaire [Lewis 2005] and hot flash assessment, have fasting blood obtained for biomarkers as well as to assure reasonable normal organ function. Key symptoms assessed at baseline will be hot flashes. Forty women will be entered on the treatment portion of the trial and will take Duavee® one tablet daily. Drug will be supplied by Pfizer. After 6-8 months of study agent, biomarkers will be reassessed. Mammogram, DEXA for body composition, RPFNA, and blood draw will be repeated. A complete side effects assessment will be performed. Entry of 40 women should allow 36 women to complete the study and be evaluable for the primary endpoint. Trial accrual is anticipated to take 6 months with completion of clinical aspects of the study by 12 months. Since this is not a blinded study, analysis of feasibility and changes in Ki-67 can take place immediately.

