4.3 Inclusion Criteria for Intervention Phase

4.3.1 RPFNA Results: An RPFNA performed less than six months prior to enrollment on study that exhibits at least 500 cells on the cytology or Ki-67 slide, and a Ki-67 positivity measured on at least 500 cells that is less than 4%.

4.3.2 Baseline chemistry profile showing reasonably normal renal and hepatic function. Creatinine <2.0, Bilirubin < 2.5, and albumin > 3.4

4.3.3 Willingness to comply with study procedures.

- Willing to have a blood draw for serum to archive bioavailable estradiol, SHBG, FSH, and bazedoxifene levels as well as a chemistry profile to ensure reasonable normal organ function at baseline and 6 month visits (approximately four tubes of blood collected)
- Willing to have a DEXA scan for body composition and waist measurement at baseline and 6-8 months.
- Willing to have a repeat mammogram and RPFNA at 6-8 months following initiation of study drug
- Willing to undergo a history, physical, vitals and breast exam at baseline and 6 month visits
- Willing to be contacted by the trial coordinator at months 1 and 3 during the 6 month study period.
- Willing to complete a 29 item validated Menopause Quality of Life Intervention Questionnaire and hot flash assessment at baseline and 6 month visits
- Willing to sign and able to understand separate consents for the RPFNAs and for study participation

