13.6 Interim Analysis

There will be no formal interim analysis of the endpoints of the study. Particularly, the quantitative endpoints (other than cytomorphology and Ki-67) are routinely batch-processed at the completion of study with pre- and post-intervention samples assayed together. However, it is possible that the feasibility endpoints could be evaluated early. For example, if six participants drop out of the study early, one would not require enrolment of the full planned 40 participants to conclude that the drop-out rate of 15% was unacceptably high. If it becomes obvious that the trial will not demonstrate feasibility, then accrual to the trial can be terminated early.

Safety data will be reviewed quarterly by the KUMC KUCC Data Safety and Monitoring Committee.

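### Ki-67 slides of a pair are scored months apart with no masking to time point stated; a coded, paired read at study end would protect the 20% increase criterion at little cost

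*Combined protocol and SAP*

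**What the plan says.** **Field selection and counting (9.1.1).** "Hyperplastic ducts with the highest concentration of MIB-1 positively staining cells will be selected for analysis and 500 total ductal cells will be scored". Two technicians score separately, and a consensus score is used for analysis. Staining, apart from the hematoxylin, is automated. No coding of slides or hiding of time point is mentioned. There is one rule for slides without hyperplasia, written for one time point only: "If hyperplasia is not present in the follow-up specimen at 6 months, non-proliferative areas will be assessed".

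**Baseline timing (4.3.1).** Entry requires "a Ki-67 positivity measured on at least 500 cells that is less than 4" per cent, on an aspirate less than six months old. Hyperplasia is not required.

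**Follow-up timing (7.4).** The repeat aspirate follows six months of agent, with up to two further months allowed for scheduling.

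**No joint processing.** Section 13.6 says that "the quantitative endpoints (other than cytomorphology and Ki-67) are routinely batch-processed at the completion of study", with paired samples assayed together. Section 3 adds that "analysis of feasibility and changes in Ki-67 can take place immediately".

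**The rule applied to another biomarker (2.5).** Paired breast density assessments should be "performed by the same individual at the same setting with the rater blinded as to which image was baseline".

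**Reader agreement (2.3).** "Inter- and intra-observer variation in interpretation of staining results was low", with a Cronbach's alpha of 0.99 in an earlier study.

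**Use of the result.** Under 1.1.3 and 13.3, the criterion is met if no more than 20% of women with paired specimens show a meaningful increase. Section 13.3 ranks this first among the quantitative endpoints but secondary overall.

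**The concern.** The score depends on which ducts the reader picks, and the two picks for each woman are made months apart. As written, the reader must know that a slide is the follow-up one in order to apply the fallback to non-proliferative areas. A baseline slide without hyperplasia, which 4.3.1 permits, has no written field rule.

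There is no control arm in which a reading difference between time points would cancel. If readers expected a particular change, or if their practice drifted, the effect would enter the recorded change directly. It could produce a wrong pass or a wrong fail on the 20% criterion, and it could distort the Cohort B decrease analysis in 13.4. At stake is the signal that informs the next trial. It is not a claim of efficacy.

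**Working it through.** **1. Interval between reads.** The baseline aspirate is 0 to just under 6 months old at enrolment (4.3.1), and follow-up comes after 6 to 8 months of agent (7.4). The aspirates are therefore 6 + 0 = 6 to about 8 + 6 = 14 months apart. The baseline score must precede enrolment, so the two reads are at least about six months apart even if every follow-up slide waits until study end.

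**2. Width of the thresholds.** With 500 cells, 2% is 0.02 × 500 = 10 nuclei. Under 1.1.3 and 13.3, a woman with baseline below 1% (0 to 4 positive nuclei) counts as an increase at 10 or more. A woman at 1% (5 nuclei) counts at 2 × 5 = 10, and one at 1.4% (7 nuclei) at 14. Choice of field can plausibly move a count by a few nuclei. (Section 8.1 words the limits as strictly above 2% and above 1%, so exactly 10 of 500 is classified differently there.)

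**3. The plan's own figures.** The minimum number of pairs is 0.85 × 40 = 34, as in 13.3. The statement that an observed 10% excludes a true rate above 20% also reproduces with the simple normal interval: 0.10 + 1.96 × √(0.10 × 0.90 / 34) = 0.201. Section 3 expects slightly more pairs: "Entry of 40 women should allow 36 women to complete the study and be evaluable for the primary endpoint".

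**4. Sensitivity of the cut.** With 34 pairs, 6/34 = 17.6% passes and 7/34 = 20.6% fails. With 36 pairs, 7/36 = 19.4% passes and 8/36 = 22.2% fails. If p is the rate of increase as recorded, the exact binomial chance of passing is:

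| Recorded rate p | n = 34, P(X ≤ 6) | n = 36, P(X ≤ 7) |
|---|---|---|
| 11% | 92.7% | 96.1% |
| 15% | 75.9% | 83.8% |
| 20% | 46.6% | 56.6% |
| 25% | 21.8% | 29.0% |
| 30% | 7.9% | 11.2% |

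Between 15% and 30%, each 5-point step moves the chance of passing by 14 to 29 points at n = 34 and by 18 to 28 points at n = 36.

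**5. What a reading error would do, by assumption only.** Let m be the share of true increases read as none, and f the share of non-increases read as increases. Then recorded rate = true × (1 − m) + (1 − true) × f. The documents give neither m nor f. All results are for n = 34.
- True 25%, f = 0, m = 10, 20, 30%: the recorded rate is 22.5, 20.0, 17.5%. P(pass) rises from 21.8% to 33.0, 46.6, 61.6%.
- True 11% (the historical figure in 13.3), m = 0, f = 5, 10%: the recorded rate is 0.11 + 0.89 × 0.05 = 15.45% and 0.11 + 0.89 × 0.10 = 19.9%. P(fail) rises from 7.3% to 26.5 and 52.8%.

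**6. What masking would not remove.** With an unchanged true Ki-67 of 1.5% to 2%, counting 500 cells twice gives about a 7% chance of a recorded meaningful increase from binomial noise alone. Sampling variation and differences between staining runs also remain.

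**The case against.** The strongest reply is that no bias has been shown. The protocol is silent on masking; it does not prescribe an unmasked read. Slides may be coded under the umbrella screening protocol or the cited staining method, neither of which is available here. That stands, and it limits the point to what is written.

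A reader might take the entry under 6.11, where blinding is marked not applicable, as proof that slide readers are unmasked. It is not: that heading sits in the agent section and concerns treatment. A reader might also infer from the pass probabilities that the Ki-67 result is biased, or by how much. They do not support this. Any 20% cut with 34 or 36 pairs has these properties, whatever the source of error.

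The plan also has safeguards: an automatic stainer, a stated field rule, two readers, a consensus score and high reported agreement. These reduce random error. They do not exclude a lean that both readers share because both know the time point. Section 2.5 gives its masking advice because density is subjective, and 2.3 calls Ki-67 quantitative, so this is not a plain breach of the plan's own rule. Yet choosing the highest-staining ducts by eye is also a judgement.

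Finally, the stakes are modest. Section 13.2 disclaims conclusive proof, and 13.3 foresees a placebo-controlled trial after a pass, which would test a false pass. A false fail would have no such correction.

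**Conclusion.** The point holds as a design improvement. As written, baseline and follow-up Ki-67 are read sequentially, months apart, with no masking stated and with a fallback rule that requires knowledge of the time point. A coded, paired read is a better method, uses the same staff, and follows a principle that the protocol already states for density.

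The point does not show that the result is biased. No size or direction of reading error can be drawn from the documents. The figures show only that the 20% cut reacts strongly to small shifts: 5 points in the recorded rate, between 15% and 30%, change the chance of passing by 14 to 29 points with 34 pairs. They rest on independent women and on the 1.1.3 and 13.3 wording of the criterion. The misreading shares are assumptions.

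I rate it as cheap and worth considering, not as a correction on which the trial depends. If slides are already coded, a sentence in 9.1.1 saying so would settle the masking part. The fallback rule would still need to cover both slides.

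**What to change.** In 9.1.1:

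- Keep the real-time baseline read for eligibility and cohort membership, and retain the stained slides. Only representative images are currently said to be archived.
- Hold the off-study slides. At study end, have the same two technicians score each woman's two slides together, coded, in random order, with time point hidden.
- Use one field-selection rule, with the non-hyperplastic fallback allowed for either slide.
- Use the masked consensus scores for the increase criterion (1.1.3, 13.3) and for change in 13.4. Keep every enrolled woman with an evaluable pair, including any whose re-scored baseline is 4% or more.
- Use the masked baseline for all pairs, including those whose off-study value is imputed as 0.5% under 13.4, so that the source of the baseline does not depend on the outcome. A re-scored baseline could fall below 0.5%, so report a sensitivity analysis with the eligibility baseline score. Where the re-scored baseline is zero, report absolute change only.
- State that the historical 11% in 13.3 may have been read differently, and align the threshold wording of 8.1 with 1.1.3 and 13.3 before scoring.

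**Cost.** About 40 baseline slides are read a second time. With 34 to 40 off-study slides, the masked session covers 40 + 34 = 74 to 40 + 40 = 80 slides. No new staff, samples or procedures are needed, and the number of women and the 20% cut do not change.

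**Downsides.** Ki-67 results wait until study end, which gives up the immediate analysis in section 3. Some women may cross the 1% line on re-count, so their increase rule may differ from their accrual cohort. Staining-run differences remain. Accrual and drop-out monitoring under 13.6 is unaffected.
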